13.0 STUDY DATA COLLECTION AND SAFETY MONITORING

13.1 Data Management

This Cancer Center CTO will report clinical trial data using The Online Enterprise Research Management Environment (OnCore™), a web based Oracle® database utilizing study specific trial management tracking forms. Key study personnel are trained on the use of OnCore™ and will comply with protocol specific instructions embedded within the OnCore™ forms. Patient demographics, patient specific study treatment calendars, adverse events, reporting of deaths, and other information required for annual reporting will be placed in OnCore™ and other research databases maintained by MCW IT.

13.2 Case Report Forms

Initial Plans: Participant data will be collected using protocol specific case report forms developed by the sponsor. The CRFs will be approved by the study's Principal Investigator and the Biostatistician prior to release for use. The Study Coordinator or designee will be responsible for registering the patient at time of study entry, completing CRFs based on the patient specific calendar or roadmap, and updating the patient record until the end of required study participation.

Implementation of REDCap Database: Participant data will be collected using protocol specific electronic case report forms (e-CRFs) developed within REDCap based on its library of standardized forms. The e-CRF will be approved by the study's Principal Investigator and the Biostatistician prior to release for use. The Study Coordinator or designee will be responsible for registering the patient into REDCap at time of study entry, completing e-CRFs based on the patient specific calendar, and updating the patient record until the end of required study participation.

REDCap (Research Electronic Data Capture) is a secure web application for building and managing online surveys and databases hosted by the Medical College of Wisconsin (MCW), a CTSA consortia partner, who manages and maintains the IT infrastructure and environment in which REDCap functions. This includes the web server and database server, the communication

between those two servers, and the communication of the web server with the REDCap end-user. MCW hosts REDCap according to typical best practices with the web server and database server function two separate servers located securely behind a firewall, as required by institutional policy. Secure access requires a username/password and a Secure Sockets Layer Certificate (SSL) is in order to maintain secure communication with the end-user to login to REDCap.

This secure, web-based application designed to support data capture for research studies, providing:

1. An intuitive interface for validated data entry
2. Audit trails for tracking data manipulation and user activity
3. Automated data export and de-identification procedures for seamless data downloads to common statistical packages
4. Built-in project calendar, a scheduling module, ad hoc reporting tools
5. Advanced features – branching logic, file uploading, and calculated fields

Monitors, auditors, and other authorized agents of the United States Food and Drug Administration, as well as that of any other applicable government agencies, will be granted direct access to the study subjects' original medical records for verification of clinical trial procedures and/or data, without violating the confidentiality of the subjects, to the extent permitted by the law and regulations. In any presentations of the results of this study or in publications, the subjects' identity will remain confidential.

13.3 Data and Safety Monitoring Plan (DSMP)

The study's Data and Safety Monitoring Plan will comply with the Medical College of Wisconsin Cancer Center's Data & Safety Monitoring Plan (DSMP). For the purposes of data and safety monitoring, this study is classified as moderate risk. Therefore, the following requirements will be fulfilled:

13.3.1 Routine Reporting to the Data Safety Monitoring Committee

Study Progress Reports: The PI and Study Statistician will complete and submit a Semi-Annual Study Progress Report, every 6 months, to the MCW Cancer Center Data and Safety Monitoring Committee (DSMC) with the understanding the MCW DSMC may require more frequent reporting. Contents of the Study Progress Reports will include the information provided in the following provided table:

Table:	Content of Routine Study Progress Reports to the DSMC
---------------	--

Table: Content of Routine Study Progress Reports to the DSMC

Section 1: Protocol Administration	
 ▪ Number ▪ title ▪ PI ▪ Dates of IRB approval and activation ▪ Listing of agents, dose level, route, schedule
Section 2: Demographics	
 ▪ Number of patients enrolled ▪ M/F ▪ ages ▪ diagnoses ▪ prior treatment ▪ performance status ▪ disease status
Section 3: Phase II [per arm]	
 ▪ Dose ▪ number of patients ▪ number of courses ▪ Adverse event table with frequency and severity ▪ DLT's observed ▪ SAE's encountered ▪ Efficacy parameters: response, and biomarkers, if applicable
Section 4: SAE's	
 ▪ All SAE reports
Section 5: Patient Listing	
 ▪ Date enrolled ▪ dose level ▪ # courses ▪ maximum AE severity ▪ presence or absence of DLTs observed ▪ SAEs ▪ overall response ▪ overall outcome ▪ survival status

13.3.2 Expedited Reporting to the Data Safety Monitoring Committee

SAEs that will be assessed for trial monitoring/stopping are defined as any of the following events with possible attribution to the experimental intervention(s) (the investigational drug,

investigational device, and/or investigational therapy). This study will utilize version 4.0 of the CTCAE of the National Cancer Institute (NCI) for toxicity and performance reporting. A copy of the CTCAE version 4.0 can be downloaded from the CTEP website. Additionally, toxicities are to be reported on the appropriate case report forms.

Please note: 'CTCAE v4.0' is understood to represent the most current version of CTCAE v4.0 as referenced on the CTEP website (ie, v4.02 and all subsequent iterations prior to version 5.0). The DSMC will be notified within 5 calendars days of all serious adverse events occurring within 30 days after receipt of protocol therapy, which meets the criteria of one or more of the following:

Monitoring of Serious Adverse Events for Stopping Guidelines

1. Photosensitivity:

Skin changes of Grade 4 or higher occurring within 4 weeks of Photofrin® injection.

2. Ocular Sensitivity:

Photophobia of Grade 4 or greater occurring within 4 weeks of Photofrin® injection.

3. Neurotoxicity:

Attributing a measured decline in neurologic status to either resection or PDT will be difficult as many patients have deficits from surgical resection alone. In addition, many patients have significant neurological changes immediately post-op that improve with time and steroids. These transient neurological deficits are believed to be secondary to acute tissue injury followed by inflammation. Most transient neurological deficits improve within the first month post-op, while fixed deficits do not. Fixed deficits have a greater impact on overall quality of life. For the purposes of this study neurotoxicity will be defined as persistent neurological deficits measured at 4 weeks of Grade 4 or greater, or a decline of 2 levels (i.e. 1 to 3) when compared to pre-operative testing, recorded baseline toxicities. The study team will attempt to localize deficiencies using MRI, clinical exams and other testing (i.e. EEG) to the brain outside of the resection, but within the penumbra of the photodynamic effect (within 2 cm of the surgical field) to help with attribution (surgery versus PDT) when possible.

4. Any other hematologic or non-hematologic toxicity Grade 4 or higher.

Both progression free survival (PFS) and overall survival (OS) will be tracked.

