6.3 Photofrin® Risks and Guidelines

6.3.1 Photosensitivity

The major risk of Photofrin® skin photosensitivity sensitivity, which will persist for some time after the procedure. Risks of photosensitivity can be avoided by taking light exposure

precautions. As such, all patients who receive Photofrin® will be instructed to avoid exposure of skin and eyes to direct sunlight or bright indoor light (from examination lamps, including dental lamps, operating room lamps, un-shaded light bulbs at close proximity, etc.) for at least 30 days. Some patients may remain photosensitive for up to 90 days or more. The photosensitivity is due to residual drug, which will be present in all parts of the skin.

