7.1.3 Pharmacokinetics

Following a 2 mg kg^{-1} dose of porfimer sodium to 4 male cancer patients, the average peak plasma concentration was $15 \pm 3 \text{ mcg/mL}$, the elimination half-life was $250 \pm 285 \text{ hours}$, the steady-state volume of distribution was $0.49 \pm 0.28 \text{ L kg}^{-1}$, and the total plasma clearance was $0.051 \pm 0.035 \text{ mL min}^{-1} \text{ kg}^{-1}$. The mean plasma concentration at 48 hours was $2.6 \pm 0.4 \text{ mcg mL}^{-1}$. The influence of impaired hepatic function on Photofrin® disposition has not been evaluated.

Photofrin® was approximately 90% protein bound in human serum, studied in vitro. The binding was independent of concentration over the concentration range of $20\text{--}100 \text{ mcg mL}^{-1}$.

The pharmacokinetics of Photofrin® was also studied in 24 healthy subjects (12 men and 12 women) who received a single dose of 2 mg kg^{-1} Photofrin® given via the intravenous route. The serum decay was bi-exponential, with a slow distribution phase and a very long elimination phase. The elimination half-life was $415 \pm 104 \text{ hours}$ ($17 \pm 4.3 \text{ days}$). C_{\max} was determined to be $40 \pm 11.6 \text{ mcg/mL}$ and AUC_{inf} was $2400 \pm 552 \text{ mcg} \times \text{hour mL}^{-1}$. Women had a lower C_{\max} and a higher AUC. The clinical significance of these differences is unknown. T_{\max} was approximately 1.5 hours in women and 0.17 hours in men. At the time of intended photoactivation 40-50 hours after injection, the pharmacokinetic profiles of Photofrin® in men and women were similar.

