12.6.1 Additional Protocol Specific Reporting Requirements

12.6.1 Reporting to the Medical College of Wisconsin/Froedtert Hospital IRB

The Principal Investigator will submit timely reports to the MCW/FH IRB including any unanticipated problems, serious adverse device and drug events occurring during the investigation, and any deviation from the investigational plan, either unintentional or made to protect the life or physical wellbeing of a subject in an emergency. Any UPIRSO's, Internal Adverse Events, Adverse Device or Drug Effects, or other events meeting the MCW/FH IRB prompt reporting criteria will be reported no later than 5 calendar days after the study team becomes aware of the problem, event or information. All other adverse events will be reported at time of continuing review in accordance with MCW/FH IRB policy. Non-serious Adverse Events (collected from Day 0 to Day +30/1-Month follow-up) and non-serious/administrative protocol deviations will be collected and reported on an annual basis as per MCW/FH IRB policy. SAEs (collected from Day 0 to Day +90) that are unrelated to the study will be reported to the IRB on an annual basis via the DSMC Study progress reports. Refer to section 13.3 for details. SAEs require DSMC expedited review will be reported to the IRB within 5 calendar days.

12.6.2 Reporting to Pinnacle Biologics, Inc.

The industry collaborator, Pinnacle Biologics, Inc. is an international company with obligations in several European countries to quickly report all SAEs from all ongoing clinical trials using Photofrin®. We have developed a reporting plan that will facilitate Pinnacle's reporting requirements while safeguarding patient's confidentiality.

Reporting Serious AEs:

The investigator will report each SAE, regardless of causality, within 24 hours of awareness by

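### The safety windows disagree (4 weeks, 30 days, 90 days or none), so related late skin and eye events miss items 1 and 2, related SAEs after Day 30 lack an expedited DSMC route, and the boundary count is unclear

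*Combined protocol and SAP*

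**What the plan says.** Section 13.3.2 opens with a definition that has no time limit: "SAEs that will be assessed for trial monitoring/stopping are defined as any of the following events with possible attribution to the experimental intervention(s". The 5-day DSMC notice that follows is limited to "serious adverse events occurring within 30 days after receipt of protocol therapy, which meets the criteria" of one or more of four items:

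- Item 1: "Skin changes of Grade 4 or higher occurring within 4 weeks of Photofrin® injection".
- Item 2: "Photophobia of Grade 4 or greater occurring within 4 weeks of Photofrin® injection".
- Item 3: "neurotoxicity will be defined as persistent neurological deficits measured at 4 weeks of Grade 4 or greater", or a two-level decline from the pre-operative assessment.
- Item 4: a catch-all for remaining toxicity of Grade 4 or above, with no window of its own.

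Section 13.3.4 holds the only boundary table: 2 patients among the first 6, 3 by 12, 4 by 18 and 5 by 30. It says SAEs are reported by 4 weeks after PDT, citing 13.3.1 or 13.3.2. The table's footnote counts patients with an SAE attributed to the protocol and gives no window. Section 13.3.3 makes the boundary a prompt for DSMC consultation, not a mandatory stop.

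Other sections run longer. Section 12.6.1 refers to "SAEs (collected from Day 0 to Day +90"), in a sentence about unrelated SAEs. Section 12.3.1 sends related SAEs on Days 31-90 to the sponsor-investigator within 24 hours. Appendix 1 requires Grade 3-5 reporting for Weeks 5 to 13. Section 6.3.1 says: "Some patients may remain photosensitive for up to 90 days or more".

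**The concern.** A boundary of 2 to 5 patients is sensitive to each patient counted, so the counting rule has to be unambiguous. Here two people holding the same data could reach different counts: one closes the count at about four weeks, the other follows the footnote and includes any attributed SAE.

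The skin and ocular items raise a further point. They concern the drug's principal known hazard, which the protocol says can last 90 days or more, yet they stop at 4 weeks, before the minimum 30-day light precautions end (5.1.3, 6.3.1). Because the boundary exists only to bring the DSMC in, a late or incomplete count defeats its purpose.

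**Working it through.** **1. Windows on one clock.** Injection is Day 0 and PDT is Day 1.

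| Rule | Ends |
|---|---|
| Items 1 and 2, 4 weeks from injection | Day 28 |
| Item 3, measured at 4 weeks | about Day 28-29 |
| 13.3.4, reported by 4 weeks after PDT | 1 + 28 = Day 29 |
| 5-day DSMC notice, 30 days after protocol therapy | Day 30 from injection, 31 from PDT |
| Item 4; stopping-SAE definition; 13.3.4 footnote | none of their own |
| SAE collection (12.6.1); related SAEs to sponsor (12.3.1) | Day 90 |

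**2. Two related Day 45 events.**
- Grade 4 skin reaction: outside item 1 (45 > 28) and outside the 5-day notice (45 > 30). It reaches the sponsor-investigator in 24 hours. The stated DSMC route is the 6-monthly report (13.3.1). The footnote alone would count it; item 1 would not.
- Grade 4 thromboembolism: fits item 4 by type, but gets no 5-day notice. It counts under the footnote, and not if the 4-week or 30-day limit governs the count.

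**3. What the choice of window does to the boundary.** The documents give no target SAE rate and no operating characteristics for the boundary, so there is no stated figure to reproduce. (The separate power table in 10.2 does reproduce: at least 14 of 29 gives exact one-sided size 0.098 and power 82.0% at 55%. It is unaffected.)

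Method: exact patient-by-patient recursion. Let x(n) be the boundary after n patients with a completed window, p the per-patient probability of a counted event, and f_n(k) the probability of k events with no trigger so far.

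- f_n(k) = (1 − p) f_{n−1}(k) + p f_{n−1}(k − 1), for k < x(n)
- P(trigger) = sum over n = 1 to 30 of p f_{n−1}(x(n) − 1)

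Assumptions, not document figures: e is the probability of an attributed event by about 30 days; l is the probability of a first attributed event on Days 31-90 among the rest. The early count uses p = e. The Day +90 count uses p = e + (1 − e)l; for example 0.05 + 0.95 × 0.05 = 0.0975.

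| e | l | p to Day 90 | Trigger, early count | Trigger, Day +90 count |
|---|---|---|---|---|
| 5% | 2% | 6.9% | 5.3% | 11.3% |
| 5% | 5% | 9.75% | 5.3% | 24.8% |
| 5% | 10% | 14.5% | 5.3% | 52.8% |
| 10% | 5% | 14.5% | 26.2% | 52.8% |
| 10% | 10% | 19.0% | 26.2% | 75.4% |
| 15% | 5% | 19.25% | 55.7% | 76.4% |

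The rise is 6 points in the first row (11.3 − 5.3) and 49 in the fifth (75.4 − 26.2).

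**4. Open follow-up.** At 10 patients a year, one enrols every 365/10 = 36.5 days. On average 30/36.5 = 0.8 patients have an open 30-day window, against 90/36.5 = 2.5 with a 90-day window.

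**The case against.** A reader might infer that related SAEs on Days 31-90 never reach the boundary. The documents do not support that. The 30-day phrase governs the 5-day notice; the stopping-SAE definition, item 4 and the footnote carry no window, so a late related SAE can be read as countable. Section 13.3.4 also cites 13.3.1, whose semi-annual report includes every SAE report, and the DSMC may ask for more frequent reporting. Late related events reach the sponsor-investigator within a day. All of this stands, and it narrows the point. It does not change the wording of items 1 and 2 or the 30-day notice limit.

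A reader might also argue from pharmacokinetics. Section 7.1.3 gives a half-life of 415 hours in 24 healthy subjects, which by simple decay leaves 0.5^(672/415) = 33% at Day 28. It also gives 250 ± 285 hours in 4 cancer patients, which leaves 0.5^(672/250) = 16%. The choice moves the answer twofold and the decay is described as bi-exponential, so I do not rely on it. Nor does the 4-week window see only shielded patients: it includes operating-room light, pulse oximetry and encouraged ambient indoor light (6.2.2, 6.3.3).

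Finally, late qualifying events may be rare. Section 6.4 describes mostly mild to moderate skin reactions, and no direct serious complications of PDT in the 136-patient series. That is a fair reason not to read the trigger figures as predictions.

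**Conclusion.** The point holds as an inconsistency with three consequences. By their own wording, items 1 and 2 leave out a related Grade 4 skin or eye event after week 4. A related qualifying SAE after Day 30 has no expedited DSMC route and may wait up to about six months. Whether other late related SAEs count toward the boundary is not settled.

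The size cannot be taken from the documents. Under the assumed rates above, the choice of window moves the trigger probability by 6 to 49 points. That shows the window needs to be fixed in advance; it does not show that the early count misses a known number of events. Because the boundary prompts consultation only and the late SAEs are already collected, this is an inexpensive improvement to oversight. It does not affect the efficacy analysis.

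**What to change.** Reconcile 12.6.1, 13.3.2 and 13.3.4 by stating one counting window for the boundary, with its start day, and one DSMC route for related SAEs on Days 31-90.

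Aligning both with the existing Day 0 to Day +90 collection needs no new data:
- Extend the 5-day DSMC notice to qualifying SAEs of possible or greater attribution through Day +90.
- Make the item 1 and 2 windows consistent with that, and put the window in the table footnote.
- Keep the Week 4 neurological assessment, and say whether a related neurological decline first arising after Week 4 counts, and under which item.
- Restate the boundary's operating characteristics for the chosen window over a range of rates, and confirm or recalibrate the boundary.

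Costs to state: a few more DSMC notices; a count that is final at Day 90 for each patient, with about 2.5 patients open at a time instead of 0.8; attribution after Day 30 confounded by other anticancer therapy, which 5.2.2 allows from 1 month; and more frequent triggering at modest event rates if the boundary is unchanged.

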13.3.3 Interim Analysis and Stopping Guidelines

There will be no interim analysis for efficacy (i.e., overall survival endpoint). Monitoring for the safety endpoint of SAE occurrence related to Photofrin®, as determined by the PI, will be conducted as described in the next section. If rates significantly exceed pre-set thresholds, the Data and Safety Monitoring Committee (DSMC) will be consulted. The stopping guidelines serve as a trigger for consultation with DSMC for additional review, and are not formal “stopping rules” that would mandate automatic closure of study enrollment.

13.3.4 Safety Monitoring and Stopping Guidelines

To ensure the safety of patients on study, SAEs will be reported by 4 Weeks post PDT as defined in section 13.3.1 or section 13.3.2. The 6-month relapse free survival status will be determined based on radiological assessment as defined by section 11 and standard of care medical exam carried out at Week +24. Expected enrollment is 30 patients over the course of 3 years. The stopping guidelines are summarized in the table below.

Table: Stopping Guideline for Dose Limiting Toxicities or 6-month Relapse Free Survival

Number of patients (n)	Stopping boundary (x)
1-6	2
7-12	3
13-18	4
19-30	5

** Stopping guideline is triggered if $\geq x$ patients out of n experience a SAE with attribution to the protocol*

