2.6.3 Styli and Kaye *et. al.*: PDT 3 Year Survival Analysis

Clinical studies by Styli and Kaye *et al.*⁴ report on hematoporphyrin derivative (HpD) mediated-PDT that had been investigated as an adjuvant treatment for cerebral high-grade glioma. The study recorded the survival of patients at the Royal Melbourne Hospital, utilizing the Victorian Cancer Registry database for patients treated with adjuvant PDT following surgical resection of the tumor. For primary (newly diagnosed) tumors, median survival from initial diagnosis was 76.5 months for anaplastic astrocytoma (AA) and 14.3 months for glioblastoma multiforme (GBM). 73% of patients with AA and 25% with GBM survived longer than 36 months. For recurrent tumors, median survival from the time of surgery was 66.6 months for AA and 13.5 months for GBM. 57% of patients with recurrent AA and 37% of patients with recurrent GBM survived longer than 36 months. Younger patients (< 40) had even better survival. These survival data for high-grade glioma patients are superior to the current published survival rates in adult as well as pediatric studies. Laser light doses above the sample median of 230 J cm⁻² were associated with better prognosis in the 136 patients studied. There was no mortality directly associated with the therapy; three

patients had increased cerebral edema thought to be related to PDT that was controlled with conventional therapies. No patients had permanent neurological deficit. Of the 29 patients who received chemotherapy, no association between the use of chemotherapy and prognosis following PDT was found.

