12.2 Expedited Reporting Requirements

See Next Page...

12.2.1 Adverse Events that Occur on Studies under an IND/IDE within 30 Days of the Last Administration of the Investigational Agent/Intervention¹

FDA REPORTING REQUIREMENTS FOR SERIOUS ADVERSE EVENTS (21 CFR Part 312)

NOTE: Investigators **MUST** immediately report to the sponsor **ANY** Serious Adverse Events, whether or not they are considered related to the investigational agent(s)/intervention (21 CFR 312.64)

An adverse event is considered serious if it results in **ANY** of the following outcomes:

- 1) Death
- 2) A life-threatening adverse event
- 3) An adverse event that results in inpatient hospitalization or prolongation of existing hospitalization for ≥ 24 hours
- 4) A persistent or significant incapacity or substantial disruption of the ability to conduct normal life functions
- 5) A congenital anomaly/birth defect.
- 6) Important Medical Events (IME) that may not result in death, be life threatening, or require hospitalization may be considered serious when, based upon medical judgment, they may jeopardize the patient or subject and may require medical or surgical intervention to prevent one of the outcomes listed in this definition. (FDA, 21 CFR 312.32; ICH E2A and ICH E6).

ALL SERIOUS adverse events that meet the above criteria **MUST** be immediately reported to the Sponsor-Investigator within the timeframes detailed in the table below.

Hospitalization	Grade 1 and Grade 2 Timeframes	Grade 3-5 Timeframes
Resulting in Hospitalization ≥ 24 hrs.	10 Calendar Days	Initial Report: 24-Hours Full Report: 5 Calendar Days
Not resulting in Hospitalization ≥ 24 hrs.	Not required	

Expedited AE reporting timelines are defined as:

- “24-Hour; 5 Calendar Days” - The AE must initially be reported within 24 hours of learning of the AE, followed by a complete expedited report within 5 calendar days of the initial 24-hour report.
- “10 Calendar Days” - A complete expedited report on the AE must be submitted within 10 calendar days of learning of the AE.

¹Serious adverse events that occur more than 30 days after the last administration of investigational agent/intervention and have an attribution of possible, probable, or definite require reporting as follows:

Expedited 24-hour notification followed by complete report within 5 calendar days for:

- All Grade 3, 4, and Grade 5 AEs

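### The 13.3.4 safety guideline has no separate trigger for treatment-related death, so up to four such deaths in 30 patients can stay below it

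*Combined protocol and SAP*

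**What the plan says.** The table in section 13.3.4 is the only numeric safety boundary. Its title is "Stopping Guideline for Dose Limiting Toxicities or 6-month Relapse Free Survival", but its footnote counts patients with an attributed SAE and nothing else: the guideline is triggered if at least x "patients out of n experience a SAE with attribution to the protocol". The boundary is 2 for 1–6 patients, 3 for 7–12, 4 for 13–18 and 5 for 19–30. The same section plans for 30 patients.

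Death is one of the outcomes that make an event serious under section 12.2. Section 13.3.2 lists the events monitored for the guideline: photosensitivity, photophobia, persistent neurotoxicity, and "Any other hematologic or non-hematologic toxicity Grade 4 or higher". A Grade 5 event therefore shares a class with Grade 4, and death has no line of its own.

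Section 13.3.3 says what crossing the boundary does: "The stopping guidelines serve as a trigger for consultation with DSMC for additional review". It does not close enrolment automatically. Attribution rests with the investigator: "Monitoring for the safety endpoint of SAE occurrence related to Photofrin®, as determined by the PI".

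The DSMC also hears of events by other routes:

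- Section 13.3.2: notice within 5 calendar days of each listed SAE with possible attribution that occurs within 30 days of protocol therapy.
- Section 12.6.1: mentions expedited DSMC review of some SAEs, without defining it. It also sets SAE collection from Day 0 to Day +90.
- Section 13.3.1: a progress report every six months with all SAE reports. The DSMC may ask for reports more often.

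**The concern.** PDT is added to a resection that these patients would have anyway. The protocol's safety case leans on a series of 136 patients (section 2.6.3), of which it says "There was no mortality directly associated with the therapy". Against that background, a death judged possibly related to the drug, device or illumination is the most informative safety event the trial could produce. Yet in the count it equals a Grade 4 laboratory toxicity, and a single one never reaches the boundary at any sample size.

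What is at stake is whether the DSMC's deliberation on such a death is planned or left to discretion. The gap is widest after day 30. Section 12.3.3 anticipates possibly related deaths between 30 and 90 days and requires them to be reported within 24 hours, but section 12.3 is about reporting to the sponsor-investigator. The 5-day DSMC notice does not extend that far. Section 13.3.4 has SAEs reported by 4 weeks after PDT, so it is not even clear that a later death enters the count.

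**Working it through.** **The plan's own figure.** The documents give no acceptable SAE rate, error rate or method for the boundary, so it cannot be re-derived. It is taken as stated: 2 / 3 / 4 / 5 at n = 1–6 / 7–12 / 13–18 / 19–30, checked after every patient, with 30 patients.

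**Step 1: what four deaths need in order to stay silent.** At most 1 in patients 1–6, at most 2 in patients 1–12 and at most 3 in patients 1–18, with no fifth patient counted. Let a, b, c and d be the deaths in patients 1–6, 7–12, 13–18 and 19–30. The silent orderings are the sum of C(6,a)·C(6,b)·C(6,c)·C(12,d) over a + b + c + d = 4 with a ≤ 1, a + b ≤ 2 and a + b + c ≤ 3.

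- a = 0: 3,045 (b = 0) + 4,776 (b = 1) + 2,070 (b = 2) = 9,891
- a = 1: 6 × (796 + 828) = 9,744
- Total: 19,635 of C(30,4) = 27,405, or 71.6%

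For example, deaths in patients 6, 12, 18 and 30 never trigger, while deaths in patients 1, 2, 20 and 21 trigger at patient 2. Five affected patients always trigger.

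**Step 2: trigger probability when related deaths are the only counted events.** The silent orderings for 0, 1, 2, 3 and 4 deaths are S = 1, 30, 420, 3,570 and 19,635. At a true related-death rate p,

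P(silent) = Σ S_m · p^m · (1 − p)^(30 − m), m = 0 to 4.

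- p = 5%: 0.2146 + 0.3389 + 0.2497 + 0.1117 + 0.0323 = 0.947, so the table triggers in 5.3% of trials.
- p = 10%: 0.0424 + 0.1413 + 0.2198 + 0.2076 + 0.1269 = 0.738, so it triggers in 26.2%.
- The same sum gives 55.7% at 15% and 79.3% at 20%.

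**Step 3: how far other SAEs close the gap.** Given four deaths, silence also needs none of the other 26 patients to have a counted event. If their rate is q (an assumption; the documents give none) and events are independent, P(silent given four deaths) = 0.716 × (1 − q)^26. This is 42% at q = 2%, 19% at 5% and 5% at 10%.

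**Step 4: comparison with the cited series.** Zero related deaths in 136, taking that series' own attribution at face value, gives a one-sided 95% upper limit of 1 − 0.05^(1/136) = 2.2%. At that rate, four or more deaths in 30 have probability 0.4%.

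**Step 5: a trigger on one death.** P(trigger) = 1 − (1 − p)^30.

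| True related-death rate | Table | Single-death trigger |
|---|---|---|
| 0.5% | not computed | 14% |
| 1% | 0.2% | 26% |
| 5% | 5.3% | 79% |
| 10% | 26.2% | 96% |

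**The case against.** The strongest reply is that the table is not the DSMC's only source. A reader might infer that four related deaths could pass without the DSMC being consulted at all, or that 13.3.3 makes the table the sole route to it. The documents do not support either reading. Section 13.3.3 calls the guidelines a trigger, not the only one. Within 30 days, four possibly related deaths would produce four individual notices under 13.3.2, and 12.6.1 mentions expedited DSMC review. Section 13.3 also binds the study to an institutional monitoring plan that is not reproduced here and may say how the DSMC acts on a notified death. All of this stands.

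It does not close the gap. In this protocol, a notice carries no required DSMC action or response time, the expedited review is undefined, and neither is shown to cover deaths after day 30.

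The second reply is that silence through four deaths needs an otherwise clean trial. That also stands, and Step 3 shows how much it matters. The boundary's behaviour with deaths alone is a limiting case, not a forecast.

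The third is that a single-death trigger may fire often. Under section 12.4, *possible* covers events that the patient's clinical state could also explain. Section 13.3.2 concedes that separating surgery from PDT is hard for neurological decline. The 14% and 26% in Step 5 are therefore at the low end if deaths from disease or surgery are rated possible. This is a real cost, and a reason not to attach an automatic hold on registration, which would also sit badly with 13.3.3.

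**Conclusion.** The concern holds in a limited form. The numeric guideline gives death no separate weight, and up to four related deaths in 30 patients can stay below it. That requires an order that is not clustered early (71.6% of orderings, all taken as equally likely) and no other patient with a counted SAE. With deaths as the only counted events, the table triggers in 5% of trials at a 5% related-death rate and in 26% at 10%. Other counted SAEs bring the trigger forward.

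Possibly related deaths within 30 days do reach the DSMC individually. What is missing is a pre-set consultation tied to them and, for days 31 to 90, any DSMC route in the protocol other than the semi-annual report. This is a worthwhile and inexpensive improvement to oversight, not a failure of the monitoring plan as a whole.

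**What to change.** Add one line under the table in section 13.3.4:

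*Independently of the table, any single death through Day +90 with possible, probable or definite attribution to the drug, device or photoillumination is notified to the DSMC within 5 calendar days and triggers DSMC consultation; whether enrolment pauses meanwhile is for the DSMC to decide.*

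Leave the table counts as they are. The Day +90 limit matches the SAE collection period in 12.6.1, the attribution wording follows the scope in 13.3.2, and the principle in 13.3.3 that nothing closes automatically is kept.

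The cost is one sentence and some extra consultations: in 14% to 26% of trials at a true related-death rate of 0.5% to 1%, and more often if deaths from disease or surgery are rated possible. No change to sample size or efficacy analysis follows.
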